8.3 ADVERSE EVENTS AND SERIOUS ADVERSE EVENTS

8.3.1 DEFINITION OF ADVERSE EVENTS

Adverse Event (AE): Any untoward or unfavorable medical occurrence in a human study participant, including any abnormal sign (e.g. abnormal physical exam or laboratory finding), symptom, or disease, temporally associated with the participants' involvement in the research, whether or not considered related to participation in the research.

8.3.2 DEFINITION OF SERIOUS ADVERSE EVENTS

Serious Adverse Event (SAE): Any adverse event that:

- · Results in death
- · Is life threatening, or places the participant at immediate risk of death from the event as it occurred
- Requires or prolongs hospitalization
- Causes persistent or significant disability or incapacity
- Results in congenital anomalies or birth defects
- · Is another condition which investigators judge to represent significant hazards

8.3.3 CLASSIFICATION OF AN ADVERSE EVENT

8.3.3.1 SEVERITY OF EVENT

Mild: Awareness of signs or symptoms, but easily tolerated and are of minor irritant type causing no loss of time from normal activities. Symptoms do not require therapy or a medical evaluation; signs and symptoms are transient.

Moderate: Events introduce a low level of inconvenience or concern to the participant and may interfere with daily activities, but are usually improved by simple therapeutic measures; moderate experiences may cause some interference with functioning

Severe: Events interrupt the participant's normal daily activities and generally require systemic drug therapy or other treatment; they are usually incapacitating

8.3.3.2 RELATIONSHIP TO STUDY INTERVENTION/EXPERIMENTAL MANIPULATION

Definitely Related: The adverse event is clearly related to the investigational agent/procedure – i.e. an event that follows a reasonable temporal sequence from administration of the study intervention, follows a known or expected response pattern to the suspected intervention, that is confirmed by improvement on stopping and reappearance of the event on repeated exposure and that could not be reasonably explained by the known characteristics of the subject's clinical state.

Possibly Related: An adverse event that follows a reasonable temporal sequence from administration of the study intervention, follows a known or expected response pattern to the suspected intervention, but a number of other factors could readily have produced that.

Not Related: The adverse event is clearly not related to the investigational agent/procedure - i.e. another cause of the event is most plausible; and/or a clinically plausible temporal sequence is inconsistent with the onset of the event; and the study intervention and/or a causal relationship is considered biologically implausible.

8.3.3.3 EXPECTEDNESS

Unexpected - nature or severity of the event is not consistent with information about the condition under study or intervention in the protocol, consent form, product brochure, or investigator brochure.

Expected - event is known to be associated with the intervention or condition under study.

8.3.4 TIME PERIOD AND FREQUENCY FOR EVENT ASSESSMENT AND FOLLOW-UP

The occurrence of an adverse event (AE) or serious adverse event (SAE) may come to the attention of study personnel during study visits or via the hotline described above. If this occurs, they will be captured on a case report form which includes the time, a description of the event or concern, and current status of the participant.

Any AEs or SAEs that are deemed unrelated to the study will not be followed up. Any AEs or SAEs deemed potentially related to the study or definitely related to the study will be tracked and monitored every two weeks throughout the study until resolved.

8.3.5 ADVERSE EVENT REPORTING

All definitely or possibly related AEs will be immediately reported to the Principal Investigator, and then he/she will immediately inform the Institutional Review Board overseeing this project. In addition, the Principal Investigator will provide an annual summary report of all adverse events to the IRB as part of the annual review and to the Federal Agency as part of the annual Progress Report. If no adverse events have occurred, the report will state, "No adverse events affecting human subjects have occurred during this project year."

In addition to the above, please note that per NIA policy, all adverse events, regardless of their seriousness, severity or relatedness to the intervention, are reportable to the NIA PO and an independent data and safety monitoring body such as a Data and Safety Monitoring Board (DSMB) or a Safety Officer (SO), if one is appointed by NIA. Semi-annual reports (for adverse events) will be reported to NIA PO.

Note that we anticipate a large number of disease-related events given the study population. These disease-related events include diseases endemic to the area (e.g. malaria, GI distress, fevers, injuries). We do not explicitly collect data on these medical concerns as they are unrelated to the goals or likely consequences of the study and hence will only report on them as brought to our attention by study participants.

We also anticipate poor mental health (e.g. high levels of depression and anxiety from baseline onward on screening surveys). These conditions are also not considered adverse events as no diagnostic activities are completed within the study, and will not be reported in this reporting process. However, mental health outcomes will be tracked and referred to counseling, following the procedures outlined above. Suicidal thoughts reported to surveyors will be tracked and reported as an adverse event.

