2.3 RISK/BENEFIT ASSESSMENT

2.3.1 KNOWN POTENTIAL RISKS

Risks Associated with Experimental Activities

As there are no changes to the lives of control individuals except their participation in brief surveys, the risks associated with control condition are no more than minimal and are similar to the ones in participants' everyday life. Treated participants will additionally work in the cash-forwork program, facing potential psychological and physical risks.

Psychological risks - we will proactively be screening all participants (both control and treatment) for poor mental health via the twice-monthly surveys. Any individuals scoring at or above the thresholds for depression recommended by [name], individuals who scores have increased beyond a threshold since baseline, or those expressing suicidal ideation, will be contacted by phone and asked if they would like to avail themselves of telephonic counseling with counselors provided by local NGOs. Again, those thresholds are a PHQ-2 score of six or a score increase of more than 2 relative to baseline. The counseling sessions are free whether or not a participant decides to continue participating in the study. In rare cases when a participant indicates thoughts of suicide, self-harm, or harm to others, Mind 'N' Health has an action protocol to, first, collect relevant details on the situation for assessment and, then, initiate follow-up actions with Ghana Health Services including in-person services at local government-run health facilities. With the participant's consent, Mind 'N' Health will also work with the individual's family to facilitate access to these additional services.

Physical risks - The sewing work provided has some risk of injury (e.g. sticking one's finger with a sewing needle), however this risk is likely lower and certainly no more than the risks faced by these individuals in other jobs (e.g. agricultural labor, collecting firewood). Surveys will also be conducted outdoors weather permitting and many dwellings are openair. Hence, the intervention is not likely to significantly alter Covid-19 exposure.

For AEs and SEAs related to health, participants will be referred to the closest government health post or hospital, depending on the severity of the event. The costs of transportation for AEs and SEAs considered related or potentially related to study participation will be covered by the study.

Risks associated with privacy

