2.3.3 ASSESSMENT OF POTENTIAL RISKS AND BENEFITS

The risks of the additional work are unavoidable as the effects of earned and unearned income may be quite different and earned income is significantly more policy-relevant. In addition, the risks to privacy are required in order to gather the data that is needed to assess the study.

The physical risks associated with the work have been minimized by choosing work that is unlikely to cause injury (stitching bags). The psychological risks have been minimized via active monitoring and referral processes as well as the increase in available in work among all treated participants prior to introducing variation or uncertainty. Because participants can always choose to not undertake any of the offered work, they can not be made worse off than in the absence of the offer. Notably, we have worked with an ethicist who specializes in participant payment/compensation – [name] (UPenn) in designing this study to ensure it meets the highest ethical standards. Finally, the privacy risks have been minimized by collecting only the needed data and developing robust data-security protocols focused on privacy and security.

The value of participation outweighs the risks because income instability is a fundamental concern in the lives of the poor. Understanding the full costs of this phenomenon would better allow policymakers to develop and promote policies to address the concern. These substantial benefits are weighed against relatively low risks to participation given the design considerations outlined above.

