8.2 SAFETY ASSESSMENTS

Participant mental health referrals

We will use the mental health data collected via study outcomes to monitor participant safety. Any individuals scoring at or above the thresholds for depression recommended by [name] (6 on the PHQ-2 scale), individuals whose scores have increased beyond a threshold of more than two since baseline, or those expressing suicidal ideation, will be contacted by phone within two days and asked if they would like to avail themselves of telephone-based counseling via a local NGO providing mental health services. Given the potential for stigma around mental health concerns in the local context, this option will be presented "as a person to talk with about any concerns that are on your mind." Counseling is phone-based to improve access as many individuals cannot travel for in-person counseling. The counseling sessions will be without charge to the participant whether or not a participant decides to continue study enrollment and regardless of study arm. Our aim is to support participants in their decision of whether to participate or not, and they should not feel concerned that their study participation is jeopardized by reporting poor mental health or other crises.

Further, in rare cases when a participant indicates thoughts of suicide, self-harm, or harm to others, Mind 'N' Health has an action protocol to, first, collect relevant details on the situation for assessment and, then, initiate follow-up actions with Ghana Health Services including in-person services at local government-run health facilities. With the participant's consent, Mind 'N' Health will also work with the individual's family to facilitate access to these additional services. We will also send a study team member in person to visit any participant expressing suicidal ideation who is not able to be reached by phone within 48 hours. This study team member will offer the counseling services in person and help the individual place the call if they are interested in accessing services.

The NGO providing the counseling is well established in the area. The minimum qualification of providers is a first degree BSc. in mental health nursing. Providers include psychologists, psychology therapists, certified counselors, and guidance and counseling experts. Services are available in all local languages that participants are expected to speak.

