9.4.2 ANALYSIS OF THE PRIMARY ENDPOINT(S)

We will use the standardized scoring approaches to all mental health outcomes, including any reversals of scale items as needed. These measures are repeated as described in the timelines previously.

ANCOVA regressions, as outlined in section 9.4.1 above, will be run to analyze the differences between experimental arms. Standard errors will be clustered by individual in all panel regressions. Results will be presented in a regression table with point estimates and standard errors. The regressions will be intention to treat (ITT) with all available data. Data will be cleaned to winsorize outliers, but no imputation will be conducted. If attrition is imbalanced, bounding exercises will be conducted. Given the rapid evolution of multiple hypothesis testing techniques, will we use state of the art techniques to adjust for multiple hypothesis testing.

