9.4.4 SAFETY ANALYSES

N/A

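### Apart from suicidal thoughts, score-based psychological worsening is kept out of adverse-event reporting and no count of it by arm is planned, because Safety Analyses is N/A

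*Combined protocol and SAP*

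**What the plan says.** Section 2.3.1 says that women in the work arms are "facing potential psychological and physical risks". It adds that "we will proactively be screening all participants (both control and treatment) for poor mental health via the twice-monthly surveys". The triggers in 2.3.1 and 8.2 are a PHQ-2 score of six, a rise of more than two since baseline, or suicidal ideation. Section 8.2 states the purpose: "We will use the mental health data collected via study outcomes to monitor participant safety".

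Section 8.3.1 defines an adverse event broadly. It covers unfavourable signs and symptoms, related or not, and requires no diagnosis. Section 8.3.5 nevertheless says of high depression and anxiety levels on the surveys: "These conditions are also not considered adverse events as no diagnostic activities are completed within the study, and will not be reported". The sentence goes on to limit this to the adverse-event reporting process. The same paragraph says that mental health is tracked and referred to counselling, and that suicidal thoughts reported to surveyors are reported as adverse events.

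The whole content of section 9.4.4 (Safety Analyses) is N/A. For the depression and anxiety endpoints, section 9.4.2 plans ANCOVA regressions: "Results will be presented in a regression table with point estimates and standard errors". Section 2.3.3 says: "Because participants can always choose to not undertake any of the offered work, they can not be made worse off" than without the offer.

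**The concern.** The protocol collects an individual-level signal of psychological worsening in every arm, Control included, and says that it serves safety. Nothing in the plan then summarises that signal by arm. The reason given in 8.3.5 is that poor mental health is expected from baseline onward and that nothing is diagnosed. A rise since baseline is different: it marks new worsening, and the definition in 8.3.1 does not depend on a diagnosis.

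A mean score says how an arm moved on average, not how many women moved the wrong way. Section 9.1 expects every work arm to do better than Control because of the added income, so a work-arm v Control mean could look favourable while a minority deteriorates. The trial assigns 1,067 women to unpredictable income. The statement in 2.3.3 about not being made worse off concerns individuals, and no planned analysis checks it at that level.

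**Working it through.** **Inputs from the documents.** Allocation is 400 to each of Control, Stable and Predictable and 1,067 to Unpredictable, with 5% attrition in every arm, two-sided 0.05 and 0.80 power (9.2). Retained: 400 × 0.95 = 380 and 1,067 × 0.95 ≈ 1,014. The flag is a PHQ-2 rise of more than two (2.3.1, 8.2).

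**Assumed inputs.** The documents give no PHQ-2 SD, no flag rate and no harmed share. I assume a 0–6 scale, an SD of 1.2 to 1.8, and the shares and rates stated below.

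**1. The plan's own figures.** MDE = (1.96 + 0.84) × √(1/n₁ + 1/n₂).
- 380 v 380: 0.203 SD (stated 0.2).
- 380 v 1,014: 0.1685 SD (stated 0.17).

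Both reproduce.

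**2. Can a mean against Control hide a worsened minority?** Let a share f worsen by 3 points (enough to cross the flag) and the rest improve by g. Taking Control as unchanged, mean shift = 3f − (1 − f)g, where negative is favourable.
- f = 0.10, g = 0.5: 0.30 − 0.45 = −0.15 points. That is 0.15/1.8 = 0.08 SD to 0.15/1.2 = 0.13 SD in the favourable direction.
- f = 0.10, g = 0.33: 0.30 − 0.297 = +0.003 points, about zero.

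In both cases 0.10 × 1,014 ≈ 101 women have worsened past the flag. The same holds at the trial's own effect size: if 10% worsen by 1 SD, the mean still shows a 0.20 SD benefit when the others improve by (0.20 + 0.10)/0.90 = 0.33 SD.

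**3. Would the planned Unpredictable v Predictable contrast see it?** Assume Predictable women improve by g, like the unharmed 90%. The gap is then (3f − (1 − f)g) + g = f(3 + g).
- g = 0.5: 0.10 × 3.5 = 0.35 points, or 0.19 to 0.29 SD over SD 1.8 to 1.2.
- g = 0.33: 0.10 × 3.33 = 0.333 points, or 0.185 to 0.28 SD.

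All exceed the stated 0.17 SD. I added the mixture variance f(1 − f)(3 + g)² to the Unpredictable arm; power with 380 v 1,014 is then 84% to 99%. The average harm would probably be seen. The number of women behind it would not.

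**4. What a flag comparison by arm could deliver.** Two-proportion test, two-sided 0.05, 380 v 1,014, with 95% CI half-width 1.96 × √(p₁(1 − p₁)/n₁ + p₂(1 − p₂)/n₂):

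| Assumed rates | Power | Half-width (points) |
|---|---|---|
| 5% v 10% | 88% | 2.9 |
| 10% v 17% | 92% | 3.8 |
| 10% v 15% | 69% | 3.7 |
| 5% v 8% | 49% | 2.8 |

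The flag can fire only if the baseline score leaves room for the rise. If 80% or 60% of women qualify (assumed), power for 5% v 10% falls to 79% or 65%. Counting any crossing over several rounds also raises the background rate, which moves the comparison towards the 10% v 15% row.

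**The case against.** Depression and anxiety are primary endpoints, compared across all arms, so leaving them out of adverse-event reporting is a defensible choice. A reader might infer three stronger things, and the documents support none of them.

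- *That the scores vanish from all safety information.* The exclusion covers only the adverse-event process. Scores still trigger referral, suicidal thoughts are reported as adverse events, and 10.1.6 says the DSMB is shown safety and efficacy by arm about four periods in. Part of 10.1.6 is not in the text available for this review, so it cannot be said that the DSMB never sees worsening counts.
- *That arm coefficients against Control are the only planned use of the scores.* Section 4.2 and its Table 4, with 9.2 and 9.4.1, plan Unpredictable v Predictable contrasts and comparisons by income realization. Section 9.4.7 interacts treatment with age, baseline psychological health and assets.
- *That the trial would report no harm if unpredictability harmed a minority.* Step 3 shows that the planned Unpredictable v Predictable contrast would probably pick up the illustrated harm.

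These points stand, and they narrow the concern. They do not remove it. Every one of these planned outcome analyses compares means, and the mid-study DSMB look is confidential and is not a final result. A pre-analysis plan is still to come, but as written 9.4.4 says N/A.

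On the remedy, section 8.1 lists no suicidality scale and 8.2 disclaims systematic adverse-event collection. Counts of suicidal thoughts therefore depend on what women report to surveyors and may not be equally complete in every arm.

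**Conclusion.** The concern holds in a limited form. Apart from suicidal thoughts, worsening as defined by the protocol's own PHQ-2 rise flag is kept out of adverse-event reporting, and no count by arm is specified. The planned mean comparisons may detect an average harm of unpredictability. They cannot give the number of women who worsened, and a work-arm v Control mean can look neutral or favourable while, under the assumed inputs, about 101 of 1,014 women cross the flag.

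The illustration rests on an assumed harmed share of 10%, a 3-point worsening and an SD of 1.2 to 1.8. It shows that masking against Control is possible, not that it is likely. A table by arm would estimate the difference to within roughly 3 to 4 points at the assumed rates if every retained woman could be counted, and less precisely once the denominator is restricted. It should be read as estimates with intervals, and a non-significant difference must not be read as evidence of safety. This is a worthwhile, inexpensive improvement. It does not threaten the primary analysis.

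**What to change.** Replace N/A in 9.4.4 with a descriptive table by arm, in all randomized women with data:

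1. The number and proportion of women with at least one in-treatment survey crossing the existing flag (PHQ-2 rise of more than two since baseline), among women whose baseline score allows it to fire. Give risk differences with 95% CIs for each work arm v Control and for Unpredictable v Predictable. State the denominator in each arm.
2. The number of women with suicidal thoughts reported as an adverse event, by arm, with a note that no suicidality scale is listed in 8.1 and that ascertainment depends on reports to surveyors.
3. Counselling referrals and acceptances by arm, where recorded.

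Report intervals, and keep the table outside the family of multiplicity-adjusted hypotheses. Reconcile 8.2 (scores monitor safety), 8.3.1 (no diagnosis needed), 8.3.5 (scores excluded because nothing is diagnosed) and 9.4.4 (N/A), so that it is clear where score-based worsening is reported. The flag serves here only as an analysis variable; the referral rule is not changed.

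Cost: a paragraph of wording and one table, with no new scores, visits or staff. The downside is a few more descriptive comparisons of limited precision.

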8.3.6 SERIOUS ADVERSE EVENT REPORTING

A summary of all SAEs will be reported to the NIA Program Officer quarterly during all times when participants are enrolled, unless otherwise requested. Additionally, SAEs will be reported to the DSMB at all meetings which follow active periods of participant enrollment.

8.3.7 REPORTING EVENTS TO PARTICIPANTS N/A

8.3.8 EVENTS OF SPECIAL INTEREST

N/A

8.3.9 REPORTING OF PREGNANCY

The study will not enroll pregnant women as pregnancy related and post-partum depression are common and unrelated to study participation. However, should a women become pregnant during the trial, she will not be excluded as these concerns are less prevalent early in the pregnancy. Hence, pregnancy will not be tracked or reported.

8.4 UNANTICIPATED PROBLEMS

8.4.1 DEFINITION OF UNANTICIPATED PROBLEMS

An Unanticipated Problem (UP) is defined as any incident, experience, or outcome that meets all of the following criteria:

- Unexpected, in terms of nature, severity, or frequency, given (a) the research procedures that are described in the protocol-related documents, such as the IRB-approved research protocol and informed consent document; and (b) the characteristics of the study population;
- Related or possibly related to participation in the research (in this guidance document, possibly related means there is a reasonable possibility that the incident, experience, or outcome may have been caused by the procedures involved in the research);
- Suggests that the research places participants or others at a greater risk of harm (including physical, psychological, economic, or social harm) than was previously known or recognized.

